5.5.2. Non-protocol Specific Procedures/Surgeries

A by-subject listing will be provided for All Treated Subjects, including but not limited to procedure/surgery name, date of procedure/surgery and indication.

6. SAFETY ANALYSIS

Safety analyses will be conducted in All Treated Subject.

Safety data will be presented in terms of study drug exposure, AEs, clinical laboratory data.

6.1. Exposure to Study Drug and Compliance

Treatment exposure will be summarized for All Treated Subjects using the following measures:

- Number of doses administered
- Descriptive statistics of duration of treatment (months), along with number of subjects with treatment duration longer than or equal to 3 months, 6 months, 12 months and 24 months; Duration of treatment (in days) will be calculated as (date of the last dose - date of the first dose + 1) and converted to months by dividing by 30.4375
- Number and percentage of subjects with dose reduction according to percentage of dose reduction and reasons for dose reduction
- Descriptive statistics of time to first dose reduction.
- Number and percentage of subjects with dose delays
- Number and percentage of subjects with infusion interruptions
- Descriptive statistics of duration of interruptions
- Relative dose intensity will be calculated as described below and summarized. Cumulative dosage and relative dose intensity will be summarized by descriptive statistics, and relative dose intensity will be additionally summarized by the category of <50%, 50% to < 70%, 70% to <90%, 90% to <110%, >=110%.

Delivered dose (mg) for each infusion is calculated per CRF form from (“Total dose to be administrated” x “Actual volume administered”)/“Total volume prepared ”).

Delivered dosage (mg/kg) of each infusion in a cycle is calculated by dividing the delivered dose (in mg) by body weight (in kg) at the beginning of the cycle (the body weight according to which the prescribed dose is calculated and prepared per the Protocol).

Cumulative dosage (mg/kg) received for each subject is defined as the sum of all delivered doses (mg/kg) of all infusions the subject received in the study.

Total assigned dosage (mg/kg) for each subject is defined as the product of the assigned dose of sacituzumab govitecan (“planned dose” per CRF form) and number of doses the subject was scheduled to receive during the subject’s treatment period (number of infusions actually received by the subject plus the number of infusions the subject missed between the first and last infusion).

Relative dose intensity (in %) for each subject is calculated: dividing the subject’s cumulative dosage received (in mg/kg) by the total assigned dosage (in mg/kg) as defined above.

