11.3.3. Safety Analyses

Safety analyses will be based on All Treated Subjects. All safety analyses will be presented by cancer types and histology when deemed appropriate. Safety data will be summarized using descriptive statistics. Categorical variables will be summarized by number and percentage. Continuous variables will be summarized using n (number of subjects with available data), mean, standard deviation, median, upper and lower quartiles, and range (minimum and maximum), unless otherwise specified.

A treatment-emergent AE will be defined as any AE that begins on or after the date of first dose of study drug up to the date of last dose of study drug plus 30 days. Treatment-emergent laboratory abnormalities will be defined as values that increase at least 1 toxicity grade from baseline at any time after baseline up to and including the date of last dose of study drug plus 30 days. Treatment-emergent AEs and SAEs and clinical laboratory test results will be summarized. Study drug exposure and concomitant medications will also be summarized.

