3. STUDY OVERVIEW

3.1. Study Design

This is an open-label, longitudinal cohort, rollover study designed to evaluate long-term safety in subjects with metastatic solid tumors that are benefiting from continuation of therapy with sacituzumab govitecan. Only subjects who continue to receive clinical benefit from continuation of sacituzumab govitecan therapy and are tolerating therapy at the time of enrollment are eligible for this study. Subjects enrolled may continue to receive sacituzumab govitecan at the dose that they were receiving in the Immunomedics-sponsored parent study at the time of consenting to participate in this rollover study. No dose escalation beyond the dose the subject was receiving in the Immunomedics-sponsored parent study at the time of consenting to participate in this rollover study is permitted. No subject will receive more than 10 mg/kg dose of sacituzumab govitecan. Subjects may continue to receive sacituzumab govitecan until they experience toxicity, disease progression or withdrawal of consent, lost to follow-up, loss of clinical benefit, or sponsor termination of the study is documented. Subjects who continued to receive sacituzumab govitecan in the parent study after disease progression (PD), may continue to receive sacituzumab govitecan until there is no clinical benefit per treating physician's assessment.

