5. STATISTICAL METHODS AND ANALYSIS

5.1. General Statistical Considerations

Endpoints and analyses pertaining to the study's primary objectives will be conducted as prescribed in respective sections of this SAP. Any notable analyses, adjustments to analyses, or analyses not conducted due to lack of data or due to other technical constraints will be noted.

All safety analyses will be analyzed in the All Treated Subjects population and presented by a single arm. When deemed appropriate, it may also be presented by dose level, cancer types and histology. Same for subgroup analysis, it may also be conducted.

Continuous data will be summarized using descriptive statistics: n (number of subjects), mean, median, standard deviation, upper and lower quartiles, and range (minimum and maximum), unless otherwise specified. Categorical data will be summarized using counts and percentages. For summary statistics, the tables will be presented by a single arm sacituzumab govitecan. In general, individual subject listings will be provided to support the tables.

All calculations and analyses will be conducted using SAS version 9.2 or higher.

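### SAP 6.1 summarises time to first dose reduction with plain descriptive statistics, so the figures describe only reduced subjects and mix reduction risk with time on drug

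*SAP*

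**What the plan says.** SAP 6.1 introduces its list with "Treatment exposure will be summarized for All Treated Subjects using the following measures". One item on the list is "Descriptive statistics of time to first dose reduction". SAP 5.1 fixes what that phrase covers: "Continuous data will be summarized using descriptive statistics: n (number of subjects), mean, median, standard deviation, upper and lower quartiles, and range". Protocol 11.3.3 gives the same set of statistics and defines the count as "n (number of subjects with available data").

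The item just before it in SAP 6.1 is "Number and percentage of subjects with dose reduction according to percentage of dose reduction and reasons for dose reduction". The same section also reports the "number of subjects with treatment duration longer than or equal to 3 months, 6 months, 12 months and 24 months", so the sponsor expects time on drug to vary widely. Treatment has no fixed length: "Subjects may continue to receive sacituzumab govitecan until they experience toxicity, disease progression or withdrawal of consent", with further reasons in Protocol 5.3 that include termination of the study by the sponsor.

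Neither document gives a time origin, a censoring rule, a competing event, or a Kaplan-Meier or cumulative-incidence method for this variable. SAP 7 defers imputation rules to a separate file, but the scope it names (adverse events, concomitant medications, other prior therapies and procedures) does not include this time. Dose reductions made in the parent study are only listed, where available (SAP 5.2).

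**The concern.** Time to first dose reduction is a time-to-event variable. Some subjects stop treatment without ever being reduced, and others may still be on drug at data cut-off. These subjects have no value to enter into a mean or a median. The SAP does not say in words that they drop out of the calculation, but its own definitions leave no other way to compute it.

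This has two consequences. The population actually summarised is the reduced subjects, although the list is headed All Treated Subjects. In addition, a late reduction can be seen only in someone still on treatment, so the median among reduced subjects moves with treatment duration even when the risk of reduction does not.

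The study's only objective is long-term safety, and SAP 2.1 names drug exposure as part of it. This is the only planned summary of when reductions happen.

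**Working it through.** The plan states no figure for this variable, so there is nothing to reproduce. The hazards below are assumptions chosen to show the behaviour of the statistic. They are not from the documents.

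**Model.** Constant monthly hazards: r for first reduction, d for leaving treatment without one.

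- Share ever reduced = r/(r+d)
- Median among reduced subjects = ln 2/(r+d)
- Cumulative incidence by month t, with leaving treatment as a competing event = [r/(r+d)] × [1 − exp(−(r+d)t)]

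**Step 1: double the reduction hazard, with d = 0.10.**

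| r | Share reduced | Median among reduced | 12-month cumulative incidence |
|---|---|---|---|
| 0.02 | 0.02/0.12 = 16.7% | 0.693/0.12 = 5.8 months | 0.1667 × (1 − e^−1.44) = 12.7% |
| 0.04 | 0.04/0.14 = 28.6% | 0.693/0.14 = 5.0 months | 0.2857 × (1 − e^−1.68) = 23.2% |

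The median moves by less than a month. The share reduced and the cumulative incidence move clearly.

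**Step 2: hold the reduction risk and change time on drug.** Set a 20% risk of reduction by 12 months in the absence of stopping, so r = −ln(0.8)/12 = 0.0186. Set d = ln 2 divided by the assumed median treatment duration.

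| Median treatment (months) | Share reduced | Median among reduced (months) |
|---|---|---|
| 3 | 7% | 2.8 |
| 6 | 14% | 5.2 |
| 12 | 24% | 9.1 |
| 24 | 39% | 14.6 |

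The reduction hazard is the same in every row, yet the median rises about five-fold. Simulation with 200 subjects and 1,000 runs gave 2.9, 5.4, 9.2 and 14.7 months. With front-loaded reductions (Weibull shape 0.5, same 20% at 12 months) the medians are 0.9, 1.7, 3.2 and 5.9 months. The pattern therefore does not need constant hazards.

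**Step 3: why this happens.** Under constant hazards the median depends on r and d only through their sum. For example, r = 0.02 with d = 0.10 and r = 0.04 with d = 0.08 both give 0.693/0.12 = 5.8 months, although 16.7% are reduced in the first case and 0.04/0.12 = 33.3% in the second.

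**Step 4: administrative stops.** Suppose half of the assumed exit hazard of 0.10 is administrative (sponsor termination or data cut-off) and independent of reduction risk. The observed share reduced and median stay at 16.7% and 5.8 months, and the crude proportion reduced by 12 months stays at 12.7%. With the administrative stops censored, the cumulative incidence is [0.02/0.07] × [1 − e^−0.84] = 0.2857 × 0.568 = 16.2%.

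**The case against.** The strongest objection is that the neighbouring item already reports the number and percentage reduced, and n accompanies the median. In Step 1 that percentage moves from 16.7% to 28.6%, about 33 against 57 subjects if 200 are treated. A reader might infer from the near-constant median that the planned output would look much the same if the reduction risk doubled. The documents do not support that, because only this one summary would look similar.

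The objection goes further. The SAP is for the final analysis. If everyone has stopped treatment for non-administrative reasons by then, cumulative incidence is simply the share reduced multiplied by the share of reduced subjects with a time up to t. In Step 1, 16.7% reduced with a median of 5.8 months means about 8.3% reduced by 5.8 months. This is correct, but it fails once subjects are still on drug at cut-off or stopped by the sponsor (Step 4). Protocol 5.3 and 14.8 allow sponsor termination, and the documents do not say how common either case will be.

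Two other strong readings are tempting:

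- **That the median mainly reflects time on treatment.** Under constant hazards this needs fewer than half of subjects to be reduced, and the documents give no rate. With r = 0.08 and d = 0.05, 0.08/0.13 = 61.5% are reduced. Moving r from 0.04 to 0.08 then cuts the median from 0.693/0.09 = 7.7 to 0.693/0.13 = 5.3 months, which is a clear response.
- **That the true median is ln 2/r, 34.7 months at r = 0.02, so that 5.8 months is badly biased.** That target supposes nobody ever stops treatment. The SAP does not state it, and the competing-risk summary proposed here does not use it.

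Finally, this is one exposure item in a single-arm study. It is not one of the primary endpoints in Protocol 11.3.1, and no test or decision rests on it.

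**Conclusion.** The point holds as a minor one. As written, the mean, median and quartiles apply only to reduced subjects and combine reduction risk with time on drug, so they cannot be read as the timing of reduction in All Treated Subjects. That part follows from the definitions in SAP 5.1 and Protocol 11.3.3 and needs no assumed rates.

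The size does need them. In the illustration, doubling the assumed reduction hazard takes 12-month cumulative incidence from 12.7% to 23.2%, while the planned median goes from 5.8 to 5.0 months. The percentage reduced shows part of that change but gives no timing, and it too depends on time on drug. The documents do not support saying that the median is dominated by treatment duration, or that the report as a whole would hide a change in risk.

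**What to change.** In SAP 6.1, replace the item with wording such as: cumulative incidence (Aalen-Johansen) of first on-study dose reduction, measured from the first rollover dose, at 3, 6, 12 and 24 months in All Treated Subjects. Treatment discontinuation for non-administrative reasons and death are competing events. Subjects still on treatment at data cut-off, or stopped by sponsor termination, are censored at that time. The four time points are those already used for treatment duration.

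Present the result also by whether the subject had already been dose-reduced in the parent study, where SAP 5.2 makes that information available. If a median is kept, label it 'among subjects with a reduction' and give n.

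Cumulative incidence still depends on how long subjects stay on drug, but it states directly what proportion of treated subjects have been reduced by each time. The cost is one extra table and a stated rule for which stops count as administrative. The exposure and disposition data already planned should be enough.

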6.2. Adverse Events

Treatment-emergent adverse events (TEAEs) are defined as any AEs that begin or worsen on or after the start of study drug through 30 days after the last dose of study drug. All AEs will be coded using Medical Dictionary for Regulatory Activities (MedDRA). The severity will be graded based on the National Cancer Institute's (NCI) Common Terminology Criteria for Adverse Events (CTCAE) v5.0. Only TEAEs will be summarized and will be referred to as AEs hereafter.

The frequency and severity of AEs, classified by MedDRA, will be summarized using MedDRA Preferred Term (PT) and System Organ Class (SOC). An AE that occurs more than once within each subject will be counted only once in the summaries, i.e., where a subject has the same adverse event, based on preferred terminology, reported multiple times, the subject will only be counted once at the preferred terminology level in adverse event summary tables. Where a subject has multiple adverse events within the same system organ class, the subject will be counted only once at the system organ class level in adverse event summary tables. When reporting adverse events by NCI-CTCAE grade, summary tables will be provided using the worst NCI-CTCAE grade.

The following AE summary tables will be provided:

- Overall Summary of Treatment-Emergent Adverse Events
- Summary of Treatment-Emergent Adverse Events by SOC and PT
- Summary of Treatment-Emergent Adverse Events Reported $\geq 10\%$ by Preferred Term
- Summary of Treatment-related Treatment-Emergent Adverse Events by SOC and PT
- Summary of Treatment-Emergent Serious Adverse Events by SOC and PT
- Summary of Treatment-Emergent Serious Adverse Events Reported $\geq 2\%$ by Preferred Term
- Summary of Treatment-related Treatment-Emergent Serious Adverse Events by SOC and PT
- Summary of Treatment-Emergent Adverse Events by Worst NCI-CTCAE Grade, SOC and PT
- Summary of Treatment-related Treatment-Emergent Adverse Events by Worst NCI-CTCAE Grade, SOC and PT
- Summary of NCI-CTCAE Grade 3 or Higher Treatment-Emergent Adverse Events by SOC and PT
- Summary of NCI-CTCAE Grade 3 or Higher Treatment-Emergent Adverse Events Reported $\geq 5\%$ by Preferred Term
- Summary of Treatment-related Treatment-Emergent Adverse Events with NCI-CTCAE Grade 3 or Higher by SOC and PT

- Summary of Treatment-Emergent Adverse Events Leading to Dose Reduction by SOC and PT
- Summary of Treatment-related Treatment-Emergent Adverse Events Leading to Dose Reduction by SOC and PT
- Summary of Treatment-Emergent Adverse Events Leading to Dose Interruption by SOC and PT
- Summary of Treatment-related Treatment-Emergent Adverse Events Leading to Dose Interruption by SOC and PT
- Summary of Treatment-Emergent Adverse Events Leading to Study Drug Discontinuation by SOC and PT
- Summary of Treatment-related Treatment-Emergent Adverse Events Leading to Study Drug Discontinuation by SOC and PT
- Summary of Treatment-Emergent Adverse Events Leading to Death by SOC and PT
- Summary of Treatment-related Treatment-Emergent Adverse Events Leading to Death by SOC and PT

The following AE listings will be provided:

- Listing of All Adverse Events
- Listing of All Treatment-Emergent Adverse Events
- Listing of All Treatment-related Treatment-Emergent Adverse Events
- Listing of Serious Treatment-Emergent Adverse Events
- Listing of Serious Treatment-related Treatment-Emergent Adverse Events
- Listing of Treatment-Emergent Adverse Events with NCI-CTCAE Grade 3 or Higher
- Listing of Treatment-related Treatment-Emergent Adverse Events with NCI-CTCAE Grade 3 or Higher
- Listing of Treatment-Emergent Adverse Events Leading to Dose Reduction
- Listing of Treatment-related Treatment-Emergent Adverse Events Leading to Dose Reduction
- Listing of Treatment-Emergent Adverse Events Leading to Dose Interruption
- Listing of Treatment-related Treatment-Emergent Adverse Events Leading to Dose Interruption
- Listing of Treatment-Emergent Adverse Events Leading to Study Drug Discontinuation
- Listing of Treatment-related Treatment-Emergent Adverse Events Leading to Study Drug Discontinuation
- Listing of Treatment-Emergent Adverse Events Leading to Death

- Listing of Treatment-related Treatment-Emergent Adverse Events Leading to Death

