1.2.2. Toxicology

In acute toxicity studies in Swiss-Webster Mice, sacituzumab govitecan at doses of up to 750 mg/kg/dose (ie, cumulative doses of up to 1500 mg/kg) caused minimal loss (<10%) in body weight. There was no evidence of hematological toxicity and no abnormal histology findings. Transient increases in hepatic transaminases were observed that returned to normal by the end of the study.

In cynomolgus monkeys, sacituzumab govitecan administered 50 mg/kg/dose (human equivalent dose [HED] = 16 mg/kg/dose) for four treatment cycles (Days 1 and 8 of a 21-day cycle) was considered a no observed adverse effect level (NOAEL) and 120 mg/kg/dose administered 3 days apart was associated with lethality. In general, the observed toxicities were dose dependent and considered reversible. Target organs included the female reproductive tract, skin

(hair loss, pigmentation), kidney (periarteritis), lymphoid organs (lymphoid depletion), bone marrow (reduced cellularity) with concomitant reductions in red cells, white cells and platelets and the gastrointestinal tract (necrosis, erosions, inflammation, fibrosis, hemorrhage, edema).

SN-38 was negative for mutagenicity in a bacterial reverse mutation test and was found to be clastogenic in an in vitro mammalian cell micronucleus test. Neither the carcinogenicity, nor effects of sacituzumab govitecan on fertility, early embryonic development or pre- and post-natal development have been assessed. However, SN-38 is a camptothecin and hence is likely carcinogenic. Furthermore, SN-38 is a known developmental toxicant.

Additional information regarding nonclinical toxicology of sacituzumab govitecan can be found in the current edition of the investigator's brochure.

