4.3. Study Procedures

Enrollment occurs upon completion of all screening procedures. Enrollment will be performed centrally by an interactive web response system (IWRS). Clear documentation as to the reason the subject was not dosed should be provided on the relevant eCRF. Unless otherwise specified, collection windows for laboratory assessments prior to dosing may be obtained up to 3 days prior to dosing. Treatment (dosing) may be permitted either 1 day before or within 7 days after scheduled visits.

An infectious disease pandemic may pose additional risks to study drug availability, the study visit schedule, and adherence to protocol-specified safety monitoring or laboratory assessments. Refer to [Appendix 2](#) for further details on the risks and risk mitigation strategy.

For safety parameters, please refer to Section [10.1](#).

Table 1. Schedule of Assessments

Phase	Pre-Treatment	Treatment			Unscheduled Visit	End of Treatment ^a	Safety Follow-up ^b	End of Study ^a
		Treatment Cycle 1 through Last Cycle (21-day cycle)		Day 8				
Period	Screening	Day 1 (includes baseline C1D1)	Day 8					
Day	Days -21 to 1							
Informed consent	X							
Inclusion and exclusion criteria	X							
Prior sacituzumab govitecan parent study	X							
Weight		X						
Hematology ^c		X	X	X	X	X		
Serum chemistry ^d		X	X	X	X	X		
Urine pregnancy test ^e	X	X		X	X	X	X	X
FSH ^f	X							
Sacituzumab govitecan administration		X	X					
Concomitant medications		Throughout Study						
SAEs ^g		Throughout Study						
AEs ^g		Throughout Study						

AE = adverse event; C1D1= Cycle 1 Day 1; FSH = follicle-stimulating hormone; SAE = serious adverse event

a End of treatment (EOT) visit approximately 30 days of the last dose of the study drug. For the definition of End of Study (EOS), refer to Section 3.6.

b For subjects of childbearing potential, the Safety Follow-up visits will be every 28 days for 6 months after study drug discontinuation. For subjects of non-childbearing potential who have ongoing AEs or SAEs at EOT, the Safety Follow-up visits will be every 6 weeks for up to 6 months after study drug discontinuation or until the criteria for EOS (Section 3.6) have been met. Subjects of non-childbearing potential who do not have ongoing AEs or SAEs at EOT will be considered as having reached EOS.

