10.2.2.2. Reporting Period for Adverse Events

Following initiation of study drug, collect all AEs, regardless of cause or relationship, until 30 days after last administration of study drug and report the AEs on the eCRFs as instructed.

All AEs and clinically significant laboratory abnormalities should be followed until resolution or until the AE is stable, if possible. Gilead may request that certain AEs be followed beyond the protocol-defined follow-up period.

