10.2.2.3. Reporting Period for Serious Adverse Events

All SAEs, regardless of cause or relationship, that occur after the subject first consents to participate in the study (ie, signing the informed consent form) and throughout the duration of the study, including the Safety Follow-up visits, must be reported on the applicable eCRFs and to Gilead Global Patient Safety. This also includes any SAEs resulting from protocol-associated procedures performed after the informed consent form is signed.

Any SAEs (including deaths; see Section 10.2.3 for exclusions) that occur during the study (including the Safety Follow-up visits detailed in the Schedule of Assessments [Table 1]) or within 30 days of the last dose of study drug or initiation of alternative therapy, whichever is later, should also be reported regardless of causality.

Investigators are not obligated to actively seek SAEs after the protocol-defined follow-up period; however, if the investigator learns of any SAEs that occur after the protocol-defined follow-up period has concluded and the event is deemed relevant to the use of study drug, the investigator should promptly document and report the event to Gilead Global Patient Safety.

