10.2.3. Reporting Deaths

Death is an outcome of an SAE and not, in itself, an SAE. When death is an outcome, the event(s) resulting in death should be reported (eg, "pulmonary embolism" with a fatal outcome). The appropriate diagnosis (ie, cause of death) should be recorded and assigned severity Grade 5. The time period for reporting AEs (including fatal AEs) continues up to 30 days after the last dose of study drug or initiation of alternative therapy, whichever is later. Deaths that occur more than 30 days after the last dose of study drug or initiation of alternative therapy, whichever is later, are to be reported if they are assessed by the Investigator as related to study drug. Fatal AEs meeting these criteria are SAEs and should be reported to the sponsor or the sponsor's designee in accordance with the timelines specified in Section [10.2.5](#).

Deaths related to progression of the underlying disease during the study will not be reported as an SAE (see Section [10.2.2.9](#)) if, in the Investigator's judgment, the event is unequivocally due to the expected course of progression of the underlying disease, and not due to another cause.

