11.3.1. Endpoints

The primary endpoints are as follows:

- Percentage of participants experiencing any AE
- Percentage of participants experiencing any SAE
- Percentage of participants experiencing any laboratory abnormality

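### Drug-related SAEs and fatal events that begin more than 30 days after the last dose are collected but enter no AE summary table, although the primary endpoint is any SAE

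*SAP*

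**What the plan says.** **Collection.** Protocol 10.2.2.2 ends collection of AEs in general 30 days after the last dose: "collect all AEs, regardless of cause or relationship, until 30 days after last administration of study drug". SAEs run longer. Under Protocol 10.2.2.3, SAEs of any cause, from consent and "throughout the duration of the study, including the Safety Follow-up visits, must be reported on the applicable eCRFs". Under Protocol 10.2.3, deaths more than 30 days after the last dose or the start of alternative therapy, whichever is later, "are to be reported if they are assessed by the Investigator as related to study drug".

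**Length of follow-up.** The footnotes to the Schedule of Assessments (Protocol 4.3, Table 1) define three groups:
- Subjects of childbearing potential: "the Safety Follow-up visits will be every 28 days for 6 months after study drug discontinuation".
- Other subjects with AEs or SAEs ongoing at EOT: "the Safety Follow-up visits will be every 6 weeks for up to 6 months after study drug discontinuation", or until they meet the end-of-study criteria.
- All remaining subjects reach end of study at the EOT visit, about 30 days after the last dose.

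**Endpoint.** Protocol 11.3.1 lists among the primary endpoints "Percentage of participants experiencing any SAE", with no time limit.

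**Analysis.** Protocol 11.3.3 defines treatment-emergent AEs as those beginning between first dose and last dose plus 30 days, and plans summaries of treatment-emergent AEs and SAEs. SAP 6.2 uses the same window, adds events that worsen within it, and says "Only TEAEs will be summarized and will be referred to as AEs hereafter". SAP 6.4 separately summarises all-cause deaths with their causes, summarises deaths within 30 days of the last dose, and lists all death information.

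**The concern.** Long-term safety is the study's only objective. The protocol collects serious events past day 30 and singles out late drug-related deaths for reporting. No AE table is planned to count what that collection yields.

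The cases at issue are the ones a reader of a safety report most wants to see: serious or fatal events that the investigator attributes to the drug. With the tables as planned, the treatment-related SAE percentage could be too low, or the table of treatment-related AEs leading to death could show zero, while the database holds a related case. The endpoint wording adds to this. A reader who sees a percentage for any SAE would not know that SAEs collected after day 30 were left out.

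**Working it through.** The plan states no figure for this point, so there is none to reproduce. The check follows one event type at a time through the planned outputs, then sizes the untabulated window.

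**1. Where each event appears**

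| Event | AE, SAE and fatal-AE tables (SAP 6.2) | AEOSI tables (SAP 6.3) | Other output |
|---|---|---|---|
| SAE beginning or worsening by day 30 | Yes | Yes, if it meets a definition | Listings |
| Event beginning by day 30, fatal later | Yes, because the rule turns on onset or worsening | Yes, if it meets a definition | SAP 6.4 death summary and listing |
| Non-fatal drug-related SAE beginning after day 30 | No | No | Listing of all AEs only |
| Drug-related fatal event beginning after day 30 | No | No | Listing of all AEs; SAP 6.4 death summary and listing |

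Every table title in SAP 6.2 carries the treatment-emergent restriction, including those for SAEs, related SAEs, Grade 3 or higher events and events leading to death. So do all the SAP 6.2 listings except the listing of all AEs. The word hereafter in the quoted sentence carries the limit into SAP 6.3. SAP 6.4 mentions causes of death but no split by relatedness.

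**2. Length of the untabulated window**

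Inputs: 6 months of Safety Follow-up (Protocol Table 1), a 30-day window (SAP 6.2) and 30.4375 days per month (SAP 6.1). Discontinuation is taken as the date of the last dose.

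- Maximum post-dose follow-up: 6 × 30.4375 = 182.6 days, about 183.
- Untabulated: 182.6 − 30 = 152.6 days, about 153.
- Share: 152.6 / 182.6 = 0.84.
- Nominal visits after day 30: days 56, 84, 112, 140 and 168 on the 28-day schedule; days 42, 84, 126 and 168 on the 6-week schedule.
- Subjects whose study ends at EOT: about 30 − 30 = 0 days of scheduled follow-up.

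**3. Effect on the any-SAE percentage (illustration only)**

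The documents give no late-SAE rate. Take N = 200, the planned maximum, and assume a share p of subjects whose only SAE is a collected late one. The chance of at least one such subject is 1 − (1 − p)^200:

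| Assumed p | Chance of at least one |
|---|---|
| 0.5% | 63% |
| 1% | 87% |
| 2% | 98% |
| 5% | over 99.9% |

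Each such subject lowers the tabulated percentage by 1/200 = 0.5 points.

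**The case against.** The strongest reply is that the SAP does what the protocol's statistics section asks. Protocol 11.3.3 sets the same 30-day cut-off and says treatment-emergent AEs and SAEs will be summarised, and collecting SAEs for longer than they are tabulated is not in itself a contradiction. This stands. A reader might infer that the SAP breaks with the protocol, and it does not. What remains is that the endpoint wording has no limit and the extra data have no summary.

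Three other stronger readings are tempting, and the documents do not support them:

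- **Late drug-related deaths disappear from the report.** They do not. A toxicity that begins by day 30 and becomes fatal later still counts as treatment-emergent, and SAP 6.4 summarises all-cause deaths without a stated time limit. SAP 6.4 does not specify its listing columns, so relatedness might appear there; the text does not promise it.
- **84% of post-treatment SAEs are missed.** The figure is calendar time, not events, and it is the maximum for subjects in Safety Follow-up. The documents do not give the size of that group.
- **The payload's carcinogenic potential means events should be expected between day 31 and month 6.** Protocol 1.2.2 says "SN-38 is a camptothecin and hence is likely carcinogenic", which makes delayed effects a fair question but says nothing about that interval. The synopsis frames the evaluation around events seen with continued therapy, and 30 days (720 hours) is about 36 of the longer stated half-life of 19.7 hours (Protocol 1.3.1.3).

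There is also a fair objection to one possible remedy. Adding only the related late SAEs to the existing all-cause tables would mix all events to day 30 with related events afterwards, under unequal follow-up. That stands, and it is why a separate table is the better course.

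**Conclusion.** The gap is real and limited. An SAE that the investigator calls drug-related and that begins after day 30 enters no AE count or percentage. If it is fatal, it also reaches the all-cause death summary, which does not undertake to show it as related. The main loss is therefore late non-fatal related SAEs.

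The untabulated share of post-dose SAE collection runs from about zero, for subjects whose study ends at EOT, to about 84%, for those followed the full 6 months. The number of events cannot be derived from the documents and is expected to be small. The conclusion assumes that SAP 6.2 and 6.3 are programmed as titled and that late SAEs reach the eCRF, as Protocol 10.2.2.3 and 10.2.5 require. It is worth correcting because this is a safety-only study, the data are already collected, and a single related case would make a zero or a percentage misleading.

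**What to change.** Leave the treatment-emergent definition and the existing tables unchanged, and make these additions:

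1. **SAP 6.2:** one summary of SAEs and fatal AEs with onset more than 30 days after the last dose, by SOC and PT, split by investigator-assessed relatedness, with the number of subjects followed beyond day 30.
2. **Footnotes** giving the number of late related cases under the treatment-related SAE table and the table of treatment-related AEs leading to death.
3. **SAP 6.4:** show relatedness in the death summary.
4. **SAP 2.1:** state whether the any-SAE endpoint counts treatment-emergent SAEs or all collected SAEs. If the latter, Protocol 11.3.3 must be brought into line.
5. **SAP Section 8**, which at present records no changes: enter the addition.

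The cost is one extra table, two footnotes, a relatedness split in the death summary and short text changes, using data already on the eCRF. The limitation is that ascertainment after EOT is active only in subjects in Safety Follow-up. The late counts should therefore be presented as descriptive, not as a rate over all treated subjects.
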